#### B&A Computer Program

A separate randomization will be generated for each of the study sites with approximately equal numbers of subjects randomized at each site (300-450) and approximately equal numbers of subjects assigned to each of the treatment groups (150-300) at each study site to meet the overall recruitment target of 750 subjects. Eligible subjects will be randomly assigned equally to one of the two treatment groups. Each randomization will balance for history of pre-term birth, smoking and number of bleeding sites. Within strata, subjects will be randomly assigned to one of the treatment groups using an encoded program or randomization schedule supplied by the Sponsor.

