2. STUDY OBJECTIVES AND DESIGN

This is a multicenter randomized, controlled, single-blind, 2-treatment, parallel group clinical trial to assess gingivitis and maternity outcomes in pregnant women who undertake an advanced daily oral hygiene program. Up to 750 subjects were to be enrolled to complete the study with a target population of approximately 600 evaluable subjects. Subjects were adult female volunteers with moderate-to-severe gingivitis who were in their late first trimester or early-to-mid second trimester of pregnancy (8-24 weeks of pregnancy).

Sufficient screening was conducted to enroll approximately 300 evaluable subjects at each of two study centers. After informed consent was obtained, the baseline measures were recorded and subjects were randomized to either: 1) an advanced oral hygiene regimen consisting of marketed rechargeable toothbrush, toothpaste, mouth rinse and floss plus oral hygiene education counseling (Regimen), or 2) regular oral hygiene with an anticavity toothpaste, regular manual toothbrush and floss (Control).

Separate randomizations were generated for each study site with approximately equal numbers of subjects randomized to both groups. Each randomization was balanced for history of pre-term birth, smoking status and number of bleeding sites.

Study-related evaluations were scheduled, where possible, as part of routine prenatal visits. Dental examinations were conducted at Baseline before study product assignment, and monthly thereafter for 3 consecutive months of study product use. Product distribution took place at the monthly visits or via shipment when the subjects were not present for the monthly evaluation. Adverse events were collected from examination and interview. Oral hygiene and prenatal knowledge and practices were assessed by survey at Baseline and Month 3 visit.

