6.4 Birth Outcome Endpoints

Null Hypothesis: There is no difference between treatment groups with respect to the mean birth outcome when an adjustment is made for baseline demographic variables (e.g. smoking, evidence of preterm birth, etc.)

Alternative Hypothesis: There is a difference between treatment groups with respect to the mean birth outcome when an adjustment is made for baseline demographic variables (e.g. smoking, evidence of preterm birth, etc.)

Statistical analyses to determine treatment differences for mean Gestational Age and mean Birth weight will be analyzed using an analysis of variance (ANOVA) model with demographic factors such as previous pre-term birth (< 37 weeks; Y/N), self-reported smoking during pregnancy (Y/N), mother's weight at delivery (in grams), Study site and treatment. Interactions of these demographic variables with treatment will also be investigated for inclusion into the model. If the interactions are not significant at the 10% level then they will be eliminated from the final model. 95% confidence intervals will also be generated on the treatment difference of the mean gestational age and mean birth weight.

If any of the data does not satisfy the normality criterion, then transformations will be considered to improve normality or analogous nonparametric methods will be employed.

In addition, gestational age will be categorized as preterm (gestational age < 37 weeks) or term (gestational age \geq 37 weeks) for subsequent analyses and tested for treatment differences using logistic regression with the same demographic factors as described above. Gestational age will also be analyzed for treatment differences as a time-to-event variable using the log-rank test (and Kaplan Meier curves) and Cox Regression (adjusting for demographics/covariates). Other categorizations may also be used to identify early preterm births: 20 to < 34 weeks (early preterm), 34 to <37 weeks (late preterm), \geq 37 weeks; or low birth weight (< 2500 grams).

The distribution of birth weight will also be generated within the following gestational age categories (< 34, 34 to <35, 35 to <36, 36 to <37, 37 to <38, 38 to <39, \geq 39 weeks) for each treatment group using box plots.

Additional subgroups may be defined for analyzing birth outcome data, such as the following:

- By Study Site
- By Race (Caucasian, Black, Other)
- By Gestational Age at enrollment (8 to \leq 12 weeks, >12 to \leq 16 weeks, >16 to \leq 20 weeks, >20 to \leq 24 weeks)

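### SAP 6.4 gives the log-rank test of gestational age no strata and names the randomised bleeding stratum in no birth-outcome model; any power loss depends on how strongly the strata predict delivery time, and the repair costs almost nothing

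*SAP*

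**What the plan says.** **Allocation.** Protocol section 10 states: "A separate randomization will be generated for each of the study sites". It continues: "Each randomization will balance for history of pre-term birth, smoking and number of bleeding sites". It also says: "Within strata, subjects will be randomly assigned to one of the treatment groups". The table in that section gives the levels as preterm history yes/no, current smoker yes/no, and bleeding sites <60 or ≥60. SAP section 2 confirms this in the past tense: "Each randomization was balanced for history of pre-term birth, smoking status and number of bleeding sites". Two sites and three two-level factors make 2 × 2 × 2 × 2 = 16 cells, allocated 1:1.

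**Analysis.** SAP 6.4 tests mean gestational age and mean birth weight with an ANOVA using "demographic factors such as previous pre-term birth (< 37 weeks; Y/N), self-reported smoking during pregnancy (Y/N"), then mother's weight at delivery, study site and treatment. The preterm (<37 weeks) logistic model takes the same factors. Gestational age as a time to event is analysed "using the log-rank test (and Kaplan Meier curves) and Cox Regression (adjusting for demographics/covariates"). No strata are given for the log-rank test, and the Cox covariates are not listed. The bleeding stratum is not named in section 6.4, nor in the interim gestational-age model in SAP section 3.

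**The concern.** Stratified allocation makes the arms more alike on the stratification factors than chance alone would. If those factors predict delivery time, the true variance of the treatment comparison falls, but the variance used by an unstratified log-rank test does not. The test then rejects too rarely under the null and has less power than the data allow. Pooling women with different delivery-time distributions also dilutes the hazard ratio.

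The ANOVA and logistic models name site, preterm history and smoking. The log-rank test takes up none of the four factors and is the one named treatment test of gestational age with no adjustment. At stake are some efficiency on the most important secondary variable and an avoidable source of disagreement between the log-rank and Cox p-values. Leaving out the bleeding stratum raises the same issue for the regression models, on a smaller scale.

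**Working it through.** **1. The plan's own figure.** SAP 6.8 states 300 per group, a variability of 4.1 (taken as an SD in weeks), a 1.1-week difference, 90% power and two-sided 5%.

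n = 2(1.96 + 1.2816)² × 4.1² / 1.1² = 292 per group. At 300 per group, power is 90.8%. The figure reproduces. It concerns a comparison of means; the documents give no hazard ratio, event count or log-rank power.

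**2. Log-rank simulation.** All of these inputs are assumptions, because the documents give no stratum effects:
- 600 women, all with an event, in permuted blocks of 4 within the 16 cells.
- Prevalences: site 50%, preterm history 15%, smoking 15%, ≥60 bleeding sites 50%.
- Treatment hazard ratio exp[−2(1.96 + 1.2816)/√600] = 0.767, which gives 90% power by Schoenfeld's formula.
- 6,000 runs per cell; Monte Carlo SE about 0.3 points for size and 0.4 for power.
- Stratum hazard ratios in the order site / preterm history / smoking / bleeding.

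| Assumed effects | Power: no strata | Power: 4 strata | Power: 16 strata | Size: none vs 4 strata |
|---|---|---|---|---|
| None (all 1) | 89.8% | 89.5% | 88.2% | 4.7% vs 5.0% |
| Weak (1.1/1.3/1.1/1.1) | 89.2% | 89.2% | 87.9% | 4.5% vs 4.7% |
| Moderate (1.2/1.6/1.3/1.2) | 88.0% | 89.0% | 88.6% | 4.5% vs 4.7% |
| Strong (1.3/2.0/1.5/1.3) | 85.6% | 87.5% | 87.9% | 4.4% vs 5.1% |
| Extreme (1.5/3.0/2.0/1.5) | 80.6% | 85.2% | 87.5% | 3.2% vs 4.1% |

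The four strata are site × preterm history. A repeat gave 89.5 vs 89.2% (none), 88.6 vs 89.0% (moderate), 86.3 vs 88.3% (strong) and 80.0 vs 85.3% (extreme). The gain from four strata is therefore −0.3 points in both runs with no effects, 0.4 to 1.0 moderate, 1.9 to 2.0 strong and 4.6 to 5.3 extreme. Size falls unmistakably below 5% only in the extreme setting.

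**3. Why four strata and not 16.** At the assumed prevalences the smallest of the 16 cells expects 600 × 0.5 × 0.15 × 0.15 × 0.5 ≈ 3 women, while the smallest of the four expects 600 × 0.5 × 0.15 = 45. With none to weak effects, 16 cells cost 1.3 to 1.6 points in the table. In a separate run of 4,000 they cost 2.4 points with no effects (88.9 vs 86.5%) and about 1.5 with weak effects (88.3 vs 86.8%).

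**4. A different outcome model.** Gestational age was drawn as 88% N(39.4, 1.3) and 12% N(30, 6), less stratum shifts, with an assumed 0.3-week treatment shift (3,000 runs). With no stratum effects, power was 59.6% unstratified vs 60.0% with four strata. With preterm-history shifts of 0.3 and 0.5 weeks, it was 60.5 vs 60.3% and 58.6 vs 59.0%. With shifts of 1 and 2 weeks (hazard ratios near 1.9 and 3.5), it was 55.0 vs 58.6% and 48.3 vs 57.4%. At the planned 1.1-week shift both tests had 100% power in every setting (500 runs).

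**5. Bleeding stratum left out of the linear model.** Let R² be the share of the remaining variance that bleeding explains. With s = √(1 − R²) and SE = 4.1 × s × √(2/300):
- size when omitted = 2[1 − Φ(1.96/s)]
- power when omitted = Φ(1.1/SE − 1.96/s)
- power when included = Φ(1.1/SE − 1.96)

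| R² | Size, omitted | Power, omitted | Power, included |
|---|---|---|---|
| 1% | 4.89% | 90.9% | 91.0% |
| 5% | 4.43% | 91.3% | 92.1% |
| 10% | 3.88% | 91.9% | 93.4% |

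With equal halves, R² = (d/4.1)²/4 for a difference of d weeks between bleeding strata. An R² of 1% needs d = 0.82 weeks; 5% needs d = 2 × 4.1 × √0.05 = 1.8 weeks, more than the treatment effect the trial was sized for.

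**The case against.** The strongest reply is that the plan already handles most of this. The stated hypothesis concerns a mean birth outcome with adjustment, and the model that tests it names three of the four factors. The log-rank test is supplementary, and the same sentence pairs it with an adjusted Cox regression. An unadjusted and an adjusted test may differ without either being wrong. The primary test is the Month 3 Löe-Silness change, so no primary conclusion is touched. All of this stands, and it keeps the point minor.

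A reader might infer that the log-rank p-value certainly has a true error rate below 5% and certainly loses power. The documents do not support that. They report no effect of any stratum on gestational age, and with none to weak effects the simulations show no loss. The larger losses in step 4 need hazard ratios near 1.9 or more and a 0.3-week treatment effect found nowhere in the plan. They vanish at 1.1 weeks.

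A reader might also infer that the Cox model leaves bleeding out. Its covariates are not listed, so this cannot be said. The list for "analysis of variance (ANOVA) model with demographic factors such as previous pre-term birth" is open-ended and would allow bleeding to be added. But allowing is not committing, and the covariate set is better fixed before unblinding.

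Finally, stratifying on two of four factors looks inconsistent. It is a compromise: it recovers most of the loss up to strong effects and avoids sparse cells. At extreme effects it leaves some conservatism (size 4.1%).

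**Conclusion.** The point stands as a minor specification gap. The analysis of birth outcomes does not fully follow the randomisation: the log-rank test has no strata, and the bleeding stratum is a named factor in no model. To the extent that the strata predict delivery time, the unstratified test is conservative. Against four strata it loses about 0 power points with none to weak effects, 0 to 1 with moderate, 2 with strong and 5 with extreme effects. Omitting bleeding from the linear model costs under about 1 point at a partial R² up to 5%.

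These sizes rest on the assumed prevalences, stratum effects, block size and treatment hazard ratio. Any error is in the conservative direction, so no extra false positives arise.

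**What to change.** In SAP 6.4:

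1. Stratify the log-rank test by site and history of preterm birth (four strata). If these factors predict nothing, the cost is about 0.3 power points; all 16 cells would cost about 1 to 2.
2. List the randomised bleeding stratum (<60 or ≥60) as a factor in the gestational-age and birth-weight models, the preterm logistic model and the Cox model, and write out the Cox covariates. If bleeding is to be left out, say why.

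The cost is SAP wording, a strata statement in the program and one degree of freedom per model. No data collection changes. The edit should be made before the treatment blind is broken.

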## 4. Inclusion Criteria

In order to be included in the study, each subject must:

- provide written informed consent prior to participation and be given a signed copy of the informed consent form;
- be at least the age of legal consent;
- be between 8 and 24 weeks of pregnancy;
- have at least 20 natural teeth:
- have moderate-to-severe gingivitis during pregnancy, including at least 30 intraoral sites with evidence of marginal gingival bleeding.

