The monthly gingivitis endpoints were the primary outcome measure, with the Month 3 evaluation being the primary time point of interest. Maternity outcome data (gestational age, birth weight, etc.) were abstracted separately from medical records as secondary variables with gestational age being of most importance. An interim analysis of the primary and secondary outcomes was performed by an independent statistician, and the target population size was adjusted. An independent Data and Safety Monitoring Board has assessed study design, conduct and outcomes at prescribed intervals with respect to study integrity, subjects' safety and evaluability.

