5.3 Birth Outcome Evaluations

For each subject, pertinent medical records were reviewed after delivery to determine maternity outcomes such as Expected Delivery Date and Birth weight. In addition, other delivery details such as delivery route, pregnancy complications, medications, etc. and neonate variables such as Apgar score, length, evidence of congenital anomalies, etc., were recorded as additional information.

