6.0. Statistical Methods and Determination of Sample Size

All statistical tests will be 2-sided tests except where noted; and any treatment difference p-values less than 0.05 will be cited as statistically significant. The analysis for the evaluable population will be considered as the primary population and the Intent-to-Treat (ITT) analyses will be considered secondary.

The primary test will be the treatment effect test for 3-month change from baseline for Löe-Silness. No adjustments for multiple testing will be employed.

All statistical tests will be carried out using SAS® version 9 (SAS Institute Inc., Cary, NC).

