- By Age (< median age vs. ≥ median age)
- Subjects who completed all monthly visits
- By Gestational Age at enrollment (8 to ≤12 weeks, >12 to ≤16 weeks, >16 to ≤20 weeks, >20 to ≤24 weeks)

Oral Hygiene questionnaire data will be summarized by treatment group at Baseline and Month 3 visits.

Additional analyses may also be performed in order to more fully understand the data.

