- Women with no labor delay medication or procedures.
- By Age group (< median age vs. \geq median age)
- Pregnancy History (previous pregnancies (Y/N))

Additional analyses may also be performed in order to more fully understand the data.

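### The optional birth-outcome subgroup of women without labor-delay treatment is mostly defined after randomisation and should not be tested as an ordinary subgroup

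*SAP*

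**What the plan says.** SAP 6.4 introduces its birth-outcome subgroups with "Additional subgroups may be defined for analyzing birth outcome data, such as the following". It then lists study site, race, gestational age at enrollment, "Women with no labor delay medication or procedures", age group and pregnancy history. The SAP does not say which treatments count as labor delay or over what period, and it gives no rationale or caution for the item.

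The other relevant statements are these.

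- **Entry.** A woman must "be between 8 and 24 weeks of pregnancy" (Protocol section 4).
- **Source of the data.** Labor-delay treatment is not among the baseline variables in SAP 5.1. The nearest source is SAP 5.3: "For each subject, pertinent medical records were reviewed after delivery to determine maternity outcomes", with "other delivery details such as delivery route, pregnancy complications, medications, etc" recorded as additional information.
- **Outcome.** Maternity outcomes are secondary variables, "with gestational age being of most importance" (SAP section 2).
- **Reporting rule.** Under SAP 6.0, "any treatment difference p-values less than 0.05 will be cited as statistically significant", and no multiplicity adjustment is made. Subgroups are not exempted.

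SAP 6.3 has a similar optional list for gingivitis. It includes "Subjects who completed all monthly visits" and women seen by the same examiner at Baseline and afterwards.

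**The concern.** By its name, labor-delay treatment is meant to postpone delivery, so receiving it is a marker of threatened early delivery. Leaving treated women out takes early-labor cases from both arms, and more from the arm that has more of them. The women who remain are then a selected set in each arm.

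The trial's premise makes this relevant. Protocol section 1 cites a non-randomised study with less preterm birth under 35 weeks in the rinse group, and a historically controlled study with a directional reduction under 37 weeks. If the regimen does reduce preterm labor, use of labor-delay treatment should differ by arm. The subgroup is therefore least reliable when the regimen works as hoped.

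At stake is how one optional result is read. It could be taken as evidence that the regimen has no effect in uncomplicated pregnancies, or be cited as a significant difference, with no sign that it differs in kind from a subgroup by age or site.

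**Working it through.** **1. The plan's own figures.** The documents state no figure for this subgroup. The planned gestational-age comparison (300 per group, SD 4.1 weeks, difference about 1.1 weeks, 90% power, two-sided 0.05) reproduces: 292 per group are needed, and 300 give 90.8% power. It is not at issue and only supplies the scale below.

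**2. When each 6.4 subgroup is fixed.**

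| Subgroup | Fixed by randomisation? |
|---|---|
| Site, race, age group | Yes |
| Gestational age at enrollment | Yes |
| Previous pregnancies | Yes |
| No labor-delay treatment | Mostly not; no time window is given |

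**3. Preterm birth, assumed rates.** Let *p* be the proportion with threatened labor, *a* the preterm risk with it, *b* the risk without it, and *f* the share of threatened labors that are treated. All four are assumptions.

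All women: *pa* + (1 − *p*)*b*, with *a* = 0.60 and *b* = 0.05.

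- Control, *p* = 0.15: 0.15 × 0.60 + 0.85 × 0.05 = 13.25%
- Regimen, *p* = 0.10: 0.10 × 0.60 + 0.90 × 0.05 = 10.5%
- Difference: 2.75 percentage points

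Subgroup: [*p*(1 − *f*)*a* + (1 − *p*)*b*] / (1 − *pf*).

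- *f* = 1: 5% v 5%, difference 0.
- *f* = 0.5: (0.045 + 0.0425)/0.925 = 9.5% v (0.030 + 0.045)/0.95 = 7.9%, difference about 1.6 points.

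The effect shrinks with partial treatment and vanishes when every threatened labor is treated.

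**4. Mean gestational age, assumed rates.** Suppose the regimen acts only by preventing threatened labor, each event costs 5.5 weeks, and labor-delay use equals threatened labor at 30% v 10%. The difference in all women is 5.5 × (0.30 − 0.10) = 1.10 weeks. In the subgroup no one has had the event, so the difference is 0.

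Now let an unmeasured frailty also raise the chance of treatment (log-odds slope 1.5 per SD, assumed) and lower gestational age by 1 to 1.5 weeks per SD. In simulation, with total SD about 4.1, the subgroup difference becomes −0.21 to −0.31 weeks while the difference in all women stays at +1.10.

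**5. No net effect on gestational age, but use differs.** The same model, with frailty effects of 1 to 2.5 weeks per SD and 300 per group before restriction, gives:

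| Use, control v regimen | Subgroup difference (weeks) | Chance of p < 0.05 |
|---|---|---|
| 10% v 5% | −0.06 to −0.14 | 5.3% to 6.9% |
| 20% v 10% | −0.10 to −0.26 | 6.0% to 11.6% |
| 30% v 10% | −0.20 to −0.51 | 8.4% to 28.8% |

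**6. Equal use in both arms.** At 10%, 20% or 30% use in each arm, the subgroup difference is zero within simulation error and the error rate is 5.0%.

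**The case against.** Much can be said for the plan.

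- **The main analyses are unrestricted.** The ANOVA, logistic, log-rank and Cox analyses in SAP 6.4 carry no labor-delay restriction and apply to the evaluable and ITT populations. SAP 6.7 already summarises labor and delivery information by arm. This stands, and it is why the point is minor.
- **Timing and cause are inferred.** The SAP does not say when or why the treatment is given. Entry runs to 24 weeks and concomitant medications are recorded at Baseline, so some use could precede randomisation. This stands too, but it is a reason to define the item.
- **The question is reasonable.** Treatment that delays labor may itself alter gestational age, so asking what happens without it is fair. Restriction does not answer that question when use depends on arm; a stated estimand for treated women would be needed, and the SAP has none. Still, outright deletion is debatable.
- **The preterm illustration is favorable to the concern.** It fixes equal risk without threatened labor, and the 2.75-point effect is only about 1.04 standard errors at 300 per group: 0.0275 / √(0.1325 × 0.8675/300 + 0.105 × 0.895/300) = 0.0275/0.0264. The trial would usually miss it. The illustration shows the mechanism and does not forecast its size.

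A reader might infer that every other listed subgroup is safe. That is true of 6.4 but not of 6.3, where the same-examiner subset is also settled after randomisation. A reader might also infer that early delivery removes women from the subset that completed all visits. The documents leave this open, since SAP 5.6.2 counts a visit as missed only while the woman is still pregnant.

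**Conclusion.** The labor-delay item is not a subgroup of the same kind as the others in SAP 6.4. It depends mostly on events after randomisation that are tied to gestational age. If the regimen changes who receives the treatment, the comparison within it is not randomised and can hide or distort the effect. If use is equal in both arms, it is unbiased.

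The size cannot be derived from the documents. Under the assumed rates the subgroup removes between roughly two fifths (2.75 to 1.6 points, half of threatened labors treated) and all of a preterm-birth effect. With no net effect on gestational age, the spurious differences are mostly modest unless use differs strongly.

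Two stronger readings are not supported. One is that the arms in this subgroup are certain to be non-comparable: that requires use to differ by arm, and the documents give no use rates. The other is that the subgroup would manufacture a benefit for the regimen: in every case examined where the regimen lowers use, the distortion goes against it.

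The consequence is minor. The subgroup is optional, the endpoint is secondary, and the primary Month 3 Löe-Silness test is not affected.

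**What to change.** 1. In SAP 6.4, take the labor-delay item out of the inferential subgroups. Alternatively, keep it as a descriptive, non-causal analysis, state which treatments count and over what time window, and exempt it from the 6.0 rule on citing significance.
2. In SAP 6.7, name labor-delay treatment explicitly in the planned by-arm labor and delivery summary, so that readers can see whether use differed.
3. State that conclusions on gestational age rest on the evaluable and ITT analyses without this restriction. The evaluable set has post-randomisation exclusions of its own, so the ITT result should stand beside it.
4. In SAP 6.3, give the same descriptive label to the two post-randomisation gingivitis subsets: all monthly visits completed, and same examiner at Baseline and afterwards.

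The cost is SAP wording, to be settled before the blind is broken, as SAP 5.5 provides. No new data collection appears to be needed. The downside is that one optional birth-outcome subgroup, and the two gingivitis subsets, lose inferential status.
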